### **4.3 Eligibility of Subjects, Exclusions and Missing Data**

All efforts will be made to avoid any missing data, especially data related to the primary endpoints. Subjects who suffer neurological death prior to one year follow up will be imputed as Raymond 3 (the worst case) in the analysis of the primary effectiveness endpoint. Regression methods will be used to impute missing endpoint data. For either the safety endpoint or the effectiveness endpoint, five separate imputed data sets will be constructed in this manner. Inferences will then be completed using pooled estimates across the five data sets. In the event that no predictor variables can be found for the regression models, missing data will be imputed by a random draw from observed data for patients with similar baseline characteristics (e.g., gender, aneurysm location, race, etc.) as those with the missing data.

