### **4.2 Sample Size Estimate and Justification**

#### Anterior Circulation Cohort:

A sample size of up to 180 subjects with intracranial aneurysms in the distal anterior circulation has been selected for this study in order to provide 153 evaluable subjects at 12 months, with an estimated 15% attrition rate. Assuming an effectiveness primary endpoint response rate of 62% (per the findings of a meta-analysis of Neuroform stent literature as performed by King et al), the expected lower bound of the exact binomial two-sided 95% confidence interval around the success rate is greater than 50%. Assuming a safety primary endpoint rate of 8%, the expected upper bound of the exact binomial two-sided 95% confidence interval around the success rate is less than 20%. A sample size of 153 evaluable subjects provides 85% power to demonstrate the effectiveness endpoint, and a power of approximately 99% to successfully demonstrate the safety endpoint given the observed rates stated above. The combined probability of the two endpoints is  $(.85) \times (.99) = .842$ .

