#### **4.6.2 Post-procedure Variables**

Stryker Neurovascular will analyze the success rate of the Neuroform Atlas™ Stent post-procedure with 95% CI. Stryker Neurovascular will also report any device malfunctions, and all available post procedure clinical outcomes as well as the immediate post procedure image score (Raymond score by Core Lab reading).

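### Five imputations leave the effectiveness verdict partly to the random seed near the 50% goal: about 4–7% of trials at the planned 62% rate if all 15% attrition is imputed

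*Combined protocol and SAP*

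**What the plan says.** Section 4.3 covers missing data for both primary endpoints. Its main method is regression: "Regression methods will be used to impute missing endpoint data". For either endpoint "five separate imputed data sets will be constructed in this manner", and "Inferences will then be completed using pooled estimates across the five data sets". If no predictors are found, "missing data will be imputed by a random draw from observed data for patients with similar baseline characteristics". One group is handled without randomness: "Subjects who suffer neurological death prior to one year follow up will be imputed as Raymond 3".

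Section 4.4 makes mITT (all subjects successfully implanted) the primary population, so an implanted subject without a 12-month result is imputed inside the analysis that decides success. Section 4.6 sets the effectiveness rule: the lower limit of a two-sided 95% Clopper-Pearson interval is compared with 50%. Section 4.2 enrols up to 180 per cohort "in order to provide 153 evaluable subjects at 12 months, with an estimated 15% attrition rate" and assumes a 62% effectiveness rate.

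The documents give no seed, no check of Monte Carlo error, and no rule for turning pooled estimates into an exact interval.

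**The concern.** Multiple imputation adds simulation noise, and that noise shrinks as the number of imputed data sets grows. If about 27 of 180 outcomes are imputed, five draws leave noise in the pooled rate larger than one patient's contribution. For results close to the goal, two analysts following Section 4.3 on the same locked data could then reach opposite conclusions. A pivotal verdict should be reproducible from the data and the plan, and the number of imputations is a stated value that costs almost nothing to raise.

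**Working it through.** **Inputs from the plan.** 180 enrolled, 15% attrition, 62% effectiveness rate (4.2); five imputations (4.3); mITT (4.4); lower limit of the two-sided 95% interval above 50% (4.6).

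**The plan's own figures.** 180 × 0.85 = 153, so 27 are missing. The stated 85% power reproduces by normal approximation: Φ((0.12 − 1.96·√(0.25/153)) / √(0.62·0.38/153)) = 85.1%. The Clopper-Pearson rule needs at least 90/153 and gives 81.4%; that gap is a separate matter.

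**Size of the noise by hand.** Take 90 successes among 153 observed. With θ drawn from Beta(90.5, 63.5), its mean is 90.5/154 = 0.588. The imputed count among 27 has variance 27 × 0.588 × 0.412 × (154 + 27)/(154 + 1) ≈ 7.64, so its SD is 2.76 patients, or 2.76/180 = 1.54 points. Averaged over m imputations, the pooled rate has a seed-to-seed SD of 1.54/√m:

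- m = 5: 0.69 points
- m = 50: 0.22 points
- m = 100: 0.15 points

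One patient in 180 is 0.56 points. The lower limit varies more than the pooled rate because the between-imputation variance is also estimated from five values. Its simulated SD under Rubin's rules is about 0.9 points at m = 5 and 0.26 at m = 50.

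**From noise to verdicts.** For each observed count x, let f(x) be the share of seeds that pass. Two seeds disagree with probability 2f(1 − f). Averaging over the binomial distribution gives the sum over x of Bin(x; 153, p) × 2f(x)(1 − f(x)). Under Rubin's rules with m = 5:

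- 90/153 passes for 82% of seeds: 2 × 0.82 × 0.18 = 30% disagreement
- 89/153 passes for 60%: 2 × 0.60 × 0.40 = 48% disagreement

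**Disagreement with five imputations, 27 of 180 missing, no predictors.**

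| Pooling and imputation | 62% | 60% | 58% |
|---|---|---|---|
| Rubin, posterior draw | 6.2–6.6% | 8.9–9.2% | 9.4–9.7% |
| Rubin, random draw from observed | 5.3–5.6% | 7.7–7.8% | 8.7% |
| Clopper-Pearson on pooled rate | 3.9–4.2% | 5.8–6.2% | 7.2–7.5% |

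Clopper-Pearson with an effective sample size gives 5.6–6.8% at 62%. At 65%, the range over all rules is 1.3–2.5%.

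**More imputations, at 62%, over the pooling rules.**

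| Imputations | Disagreement |
|---|---|
| 5 | 3.9–6.8% |
| 20 | 2.0–3.0% |
| 50 | 1.0–2.1% |
| 100 | 0.4–2.0% |

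**Sensitivity at 62%, five imputations.**

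- 18 missing: about 3.4–4.2%. With 10 missing: 2.3–2.5%.
- Logistic-regression imputation with a strong covariate, 27 missing: about 4.5% under Rubin's rules, against 5.8% with an uninformative covariate in the same simulation.
- Safety: 0.4% at an 8% event rate and 0.6% at 12%.

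**Error rates, five versus 100 imputations.**

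| | Rubin | Clopper-Pearson on pooled rate |
|---|---|---|
| Type I error at a true 50% | 2.6% vs 2.6% | 3.1% vs 3.0% |
| Power at 62% | 83.9% vs 85.5% | 86.3% vs 86.6% |

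**The case against.** The strongest reply is that disagreement compares two hypothetical runs, whereas the trial is analysed once and its error rates barely move. That stands: a reader might infer that five imputations make false success more likely, and the type I error figures show that they do not.

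A reader might also infer that the verdict flips in 6–10% of trials under the plan's own assumptions. The documents do not support that. Rubin's rules are never named, and at 62% they give only the bottom of that range. Putting the pooled rate into the plan's exact interval gives about 4%. Values near 10% need a true rate near 58%, which is not a planning input. A rate slightly under 62% is plausible, since Section 1.1 reports the Neuroform literature meta-analysis behind that assumption as 61.1%. There, Rubin pooling with posterior draws gives 7.8–8.1%.

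Twenty-seven random imputations is a high case. Neurological deaths are set to failure, and retreatment is failure by the endpoint definition, so neither adds noise. The anterior analysis is triggered at 153 evaluable subjects, which leaves the number imputed open, and the posterior cohort may stop below 180. Informative predictors would lower the figure further.

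Finally, a reader might fault the fallback for matching donors on items such as gender and race. It applies only if no predictors are found, its list of characteristics is open-ended, and nothing bars the Raymond score from the regression model.

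What remains is that five is a stated number, it leaves avoidable noise in the effectiveness verdict, and every pooling rule examined improves with more imputations.

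**Conclusion.** The point holds as a reproducibility weakness in the effectiveness analysis near the 50% goal. Its size is about 4–7% two-seed disagreement at the planned 62% rate, up to about 10% at 58–60%, and about 1–2.5% at 65%. These figures assume that all 15% attrition is randomly imputed within mITT, data are missing at random, predictors are weak and no seed is fixed in advance. They also depend on the pooling rule. Safety is not materially affected, type I error is essentially unchanged, and the power cost is at most about 2 points. The documents do not support a claim that five imputations make the trial invalid or more permissive.

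**What to change.** In Section 4.3, replace five with a larger number of imputed data sets, for example 100; 20 to 50 already removes much of the noise. State the random seed in the plan before database lock. The two changes work together: a fixed seed prevents choice among runs but leaves a near-threshold verdict arbitrary, while more imputations make it stable. Under Clopper-Pearson on the pooled rate, 100 imputations still leave about 1.5% disagreement at 62%, so the seed is worth fixing as well.

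Optionally, name the Core Lab immediate post-procedure Raymond class (Section 4.6.2) as a candidate predictor. Do not require the 2- or 6-month imaging: Section 3.10 calls for it only where site standard of care does, so it would itself be missing for many subjects.

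The cost is a short wording change and trivial computing, with no added subjects or visits. At this revision the anterior indication is already approved, so the change bears mainly on the posterior cohort, whose analysis Section 4.6 places later.

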#### **2.4.1.2 Primary Safety Endpoint**

The primary safety endpoint is:

Any major ipsilateral stroke or neurological death within 12 months.

An ipsilateral stroke will be defined as an acute episode of focal or global neurological dysfunction due to brain or retinal infarction, or due to an intracranial hemorrhage inclusive of subarachnoid, intraventricular or intraparenchymal hemorrhage, occurring in the same hemisphere as the target aneurysm.

A major ipsilateral stroke will be defined as an ipsilateral stroke that is associated with an increase of 4 or more points on the NIHSS at 24 hours after symptoms onset.

Note: For the purpose of consistency with the primary endpoint definition, strokes in the posterior circulation adjudicated as being strokes “within the treated vascular territory” will be called “ipsilateral” strokes.

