#### Posterior Circulation Cohort:

Separate analyses of these cohort data will be performed to support an indication for use in the posterior circulation.

A sample size of up to 180 subjects with intracranial aneurysms in the posterior circulation (including vertebral, basilar and posterior cerebral arteries) will also be enrolled in order to provide 153 evaluable subjects at 12 months, with an estimated 15% attrition rate. While the safety endpoint rate for posterior circulation subjects may be higher than that for the anterior circulation subjects, that rate is not expected to exceed 12%. Assuming a safety primary endpoint rate of 12%, the expected upper bound of the exact binomial two-sided 95% confidence interval around the success rate is less than 25%. A sample size of 153 evaluable subjects provides a power of approximately 99% to successfully demonstrate the safety endpoint given the observed rates stated above. Based on outcomes in the MAPS study, the effectiveness rate for posterior circulation subjects is expected to be very close to that of anterior circulation subjects. Therefore, the statement of power to demonstrate effectiveness for a sample size of 153 evaluable anterior circulation subjects also holds for a sample size of 153 evaluable posterior circulation subjects.

For the posterior circulation cohort, a Bayesian adaptive study design (“Goldilocks” approach) providing for interim analyses of accumulated data will be used to select the final sample-size. The first interim data analysis will occur once 100 posterior circulation subjects have been enrolled. Based on enrollment rates and the frequency of disease in the posterior circulation, at the time this interim analysis is performed it is estimated that primary endpoint data will be available for approximately 39 – 63 posterior circulation subjects. If, at an interim analysis, there is at least a 95% predictive probability of observing a true rate of complete occlusion that is higher than 50%, enrollment in the posterior circulation cohort will be stopped early for success. The maximum sample-size for the posterior circulation cohort will be no more than 180 subjects.

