## **4.7 Subject Accountability**

All subjects will be included in a summary of subject accountability for this study. The frequency and percentages of subjects enrolled, present at each visit, discontinuing before study completion (including reason for discontinuation) and completing the study will be presented in the final report. For subjects lost to follow-up, the date of last contact will be used to define the censor date.

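### Section 4.3 does not tie imputation of missing 12-month safety status to event-free time already observed; the fallback, or a baseline-only regression, would overstate the primary safety rate by about 1 to 2 points

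*Combined protocol and SAP*

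**What the plan says.** The primary safety endpoint (Section 2.4.1.2) is "Any major ipsilateral stroke or neurological death within 12 months". It is analysed as a proportion in the mITT population (Section 4.4), and the Clopper-Pearson upper limit is compared with 20% in the anterior cohort and 25% in the posterior cohort (Section 4.6).

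Section 4.3 gives two routes for missing data. The main route is regression imputation, with no predictors named. The fallback applies only if no predictors can be found: "missing data will be imputed by a random draw from observed data for patients with similar baseline characteristics", with gender, aneurysm location and race as examples. Both endpoints are covered: "For either the safety endpoint or the effectiveness endpoint, five separate imputed data sets will be constructed in this manner". Section 4.3 does not say when a safety outcome counts as missing, and neither route refers to time followed without an event.

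The timing information exists. Clinical contact is scheduled at discharge and at 2, 6 and 12 months (synopsis, Follow-Up Schedule). Section 3.3 asks sites to retrieve as much follow-up data as possible from subjects who leave. Section 4.7 adds: "For subjects lost to follow-up, the date of last contact will be used to define the censor date". Survival methods, however, are planned only for the period after the 12-month visit (Section 4.6, Table 7 and its third footnote). Non-neurological death is named as a competing risk only there.

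**The concern.** Imputing a 12-month status suits the effectiveness endpoint, which is a single angiographic reading. The safety endpoint accrues over the year, and a subject lost at month 6 without an event has already passed part of the risk, perhaps most of it.

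If the imputation ignores that, two things follow. The subject is given the whole 12-month risk instead of the remaining part. The donor pool is also tilted towards events: a subject with a stroke in the first week is observed whatever happens later, whereas an event-free subject enters the pool only by completing 12 months.

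Both effects raise the estimate even when drop-out has nothing to do with outcome. At stake are the accuracy of the primary safety rate, its precision, and some of the power for a criterion that each cohort must meet separately.

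**Working it through.** **Inputs from the plan.** Per cohort: 180 subjects, 15% attrition, 153 evaluable (Section 4.2; 180 × 0.85 = 153). Assumed safety rates are 8% (anterior) and 12% (posterior), with limits of 20% and 25%.

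**Inputs assumed.** The documents give neither the timing of events within 12 months nor the attrition that applies to safety data. I take a share *e* of events at the procedure, with *e* from 0 to 0.9, and the rest uniform over the year. Drop-out is *d* = 0.15, uniform over the year and independent of outcome.

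**The plan's own figure.** With 153 subjects the Clopper-Pearson rule passes with at most 20 events (anterior) or 27 (posterior). P(X ≤ 20 | 0.08) = 0.989 and P(X ≤ 27 | 0.12) = 0.985. The stated power of about 99% is reproduced.

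**Expected estimate when event-free drop-outs are filled from the observed pool.** With true rate *p*, as fractions of all implanted subjects:

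- events observed: O = p[1 − d(1 − e)/2]
- missing (lost and event-free at loss): M = d[1 − p(1 + e)/2]
- imputed estimate: O + M × O/(1 − M) = O/(1 − M)

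For p = 0.08 and e = 0: O = 0.08 × 0.925 = 0.0740; M = 0.15 × 0.96 = 0.1440; 0.0740/0.8560 = 8.6%.

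For p = 0.08 and e = 0.8: O = 0.08 × 0.985 = 0.0788; M = 0.15 × 0.928 = 0.1392; 0.0788/0.8608 = 9.2%.

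| Share of events at procedure | True 8% estimated as | True 12% estimated as |
|---|---|---|
| 0 | 8.6% | 12.9% |
| 0.5 | 9.0% | 13.4% |
| 0.8 | 9.2% | 13.6% |
| 0.9 | 9.2% | 13.7% |

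The bias is +0.6 to +1.2 points (anterior) and +0.9 to +1.7 points (posterior). The limiting case, with all events at the procedure and all drop-out late, gives 9.3% and 13.8%.

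**Remaining risk of an event-free drop-out.** This is [p(1 − e)/2]/[1 − p(1 + e)/2]. With e = 0.8 it is 0.008/0.928 = 0.9% (anterior) and 0.012/0.892 = 1.3% (posterior). The pool-based draw assigns about 9.2% and 13.6%.

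**Precision and power, by simulation** (180 subjects, five imputations, 5,000 runs per scenario, *e* from 0 to 0.8, including a late drop-out case):

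| | Pool-based imputation | Kaplan-Meier |
|---|---|---|
| SD, anterior | about 2.3 points | 2.0 to 2.1 points |
| SD, posterior | about 2.8 points | 2.4 to 2.5 points |
| Power, anterior | 97.5 to 98.6% | 99.5 to 99.8% |
| Power, posterior | 94.7 to 97.3% | 99.1 to 99.6% |

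Power for the pool-based column applies the exact limit to the pooled rate with n = 180; the plan does not say how the exact interval is combined with five data sets. If between-imputation variance is carried through an effective sample size, power is 95.6 to 97.2% and 92.7 to 95.4%. Imputation conditional on event-free time is centred on the truth, and its SD is close to that of Kaplan-Meier.

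**The case against.** The strongest reply is that the plan never commits to this error. The random draw is only the fallback. The regression predictors are unnamed, so follow-up time is neither used nor ruled out. A reader might infer that safety outcomes are imputed from baseline variables alone; the text does not say so. This stands. For the main route the defect is an omission, and the figures above describe the fallback or a baseline-only regression. The omission still matters. Adding follow-up time as an ordinary covariate would not clearly repair it, because every observed event-free subject has full follow-up; the model has to condition on being event-free at the time of loss.

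Second, the 15% is an evaluability allowance shared with an endpoint that needs a 12-month angiogram. Safety status needs none, so safety data may be missing less often. This stands too: at 10% attrition with events clustered early, a true 8% becomes 8.7% and a true 12% becomes 13.1%.

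Third, the upward direction requires drop-out unrelated to outcome. Section 4.9 recognises informative censoring in either direction, though for the post-approval phase, and Section 3.11 foresees adverse events that prevent evaluation. If event-free drop-outs carried a remaining risk above the rate imputed to them (about 9% anterior, 13 to 14% posterior), the bias would reverse, and Kaplan-Meier would understate the risk as well.

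Fourth, the decision is little affected. At n = 180, 17 events (9.4%) give an exact upper limit of 14.7% against 20%, and 25 events (13.9%) give 19.8% against 25%. A reader might infer that the safety test is invalid or could pass an unsafe device. Under non-informative drop-out the error runs the other way.

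**Conclusion.** The concern holds in a limited form. Section 4.3 extends imputation to an endpoint that accrues over time without requiring it to use event-free follow-up. Under the fallback, or a regression on baseline predictors only, the primary safety rate is overstated by about 0.6 to 1.2 points (anterior) and 0.9 to 1.7 points (posterior). That is roughly 8 to 15% in relative terms, with an SD about 7 to 15% larger than necessary. The upward direction does not need early clustering of events; clustering only increases the size.

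These figures rest on 15% attrition in the safety data, non-informative drop-out, and 0 to 90% of events near the procedure. The documents establish none of the three for this endpoint.

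The planning rates lie 12 and 13 points below the limits, so the bias rarely changes the outcome. The cost is a reported rate that is too high and roughly 1 to 5 points of safety power with the exact limit applied to the pooled rate (about 2 to 7 points if between-imputation variance is carried). One further gap remains: Section 4.3 does not say how non-neurological death before 12 months is handled, so on a literal reading a stroke could be imputed after death.

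**What to change.** Amend Section 4.3 for the safety endpoint only:

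1. Define a missing safety outcome as event-free at last contact, with last contact before day 365.
2. Under both the regression and the fallback route, impute event status only for the interval from last contact to day 365, conditional on being event-free to that date. Subjects with earlier events are then not donors for subjects known to have passed that time.
3. State how non-neurological death before 12 months is treated, so that no event is imputed after death.
4. Keep the exact-bound success rule.
5. As sensitivity checks, report a 12-month time-to-event estimate with its 95% interval and with non-neurological death as a competing event, and a tipping-point analysis for informative drop-out.

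The cost is a few sentences and modest programming. No new data are needed, because last-contact dates are already collected. The drawback is sparse information on late events: 180 × 8% = 14.4 anterior events are expected, and if 50 to 90% are early, only about 1 to 7 inform the conditional risk. The conditional model should therefore be simple.

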# **Safety and Effectiveness of the Treatment of Wide Neck, Saccular Intracranial Aneurysms with the Neuroform Atlas™ Stent System**

## **Short Study Name: ATLAS**

### **4.4 Analysis Populations**

**ITT (Intent to Treat):** All subjects who have signed the Informed Consent Form for this trial, and in whom the Neuroform Atlas™ Stent implantation procedure has been attempted (i.e., a component of the stent system was introduced into the body).

**mITT (Modified Intent to Treat):** All subjects who have signed the Informed Consent Form for this trial, and in whom the Neuroform Atlas™ Stent has been successfully implanted.

**PP (Per Protocol):** All subjects who have signed the Informed Consent Form for this trial, who have had the Neuroform Atlas™ Stent successfully implanted, and who have not been the subject of any major protocol deviations.

**Enrolled Not Treated:** All subjects who have signed the Informed Consent Form for this trial, but in whom no component of the Neuroform Atlas™ Stent System has ever been introduced into the body as part of an implantation procedure.

**PAS ITT (ITT for the PAS):** All subjects who have signed the Informed Consent Form for this trial, and in whom the Neuroform™ Atlas Stent has been successfully implanted. This cohort is identical to the mITT cohort.

**PAS mITT (Modified Intent to Treat in PAS):** All mITT subjects who have not withdrawn, died, or refused follow-up.

The primary safety and effectiveness analyses will be performed on the mITT population. The 95% Confidence Interval (CI) for each endpoint will be calculated using the exact binomial distribution. In addition, safety data will include any adverse events reported to occur among ITT subjects in whom a Neuroform Atlas™ Stent implantation procedure was attempted but did not successfully occur. For long-term follow-up, all analyses completed for the PAS mITT cohort will also be completed for the PAS ITT cohort for comparison

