### **2.6 Study Population and Source of Subjects**

Subjects over 18 years of age presenting with wide neck, intracranial, saccular aneurysms requiring treatment with stent-assisted coiling may be eligible for study participation. Potential study candidates or their legal representatives will provide informed consent prior to any data collection. A screening and enrollment log will be provided to study sites to maintain a record of all screened subjects.

Subjects will be identified and recruited by Clinical Investigators and/or their designated research staff at a maximum of up to 40 investigative sites. Clinical investigators selected to participate in the study may enroll and treat a maximum of 20% of subjects enrolled in either cohort.

Subjects who sign an IRB or EC approved consent form will be considered enrolled in the study. Any subject consented, whether treated or not, will be assigned a screening number. Subjects who consent to participate but withdraw or are found to be ineligible prior to initiation of the procedure will be considered a screening failure, and the reasons for the screening failure will be documented on the site

[figure not shown]

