# **Safety and Effectiveness of the Treatment of Wide Neck, Saccular Intracranial Aneurysms with the Neuroform Atlas™ Stent System**

## **Short Study Name: ATLAS**

screening log. In all cases where subjects are consented but not treated using a Neuroform Atlas™ Stent, replacement subjects will be enrolled. Subjects in whom an investigational procedure is attempted but stent delivery is unsuccessful will be followed through the two month follow-up visit; these subjects will be considered treatment failures but will not be evaluated for the primary endpoints at 12 months. All treated subjects with successful stent delivery and deployment will be evaluated for the primary endpoints at 12 months post-procedure.

For long-term follow-up, subjects will be asked to return for clinical follow-up visits at 2 years and 3 years ( $\pm$  6 months) post-index procedure.

The study flow is depicted in **Figure 2**.

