### **3.8.2 Implant/Procedural Steps**

As previously indicated, the Neuroform Atlas™ Stent System consists of a laser cut, nitinol, self-expanding stent preloaded over a delivery wire inside an introducer sheath. The Neuroform Atlas™ Stent System is shipped with detailed written Directions for Use (DFU). Prior to enrolling and treating a subject in the study, all Investigators will review and understand the DFU, and will be trained by the Sponsor with regards to use of the Neuroform Atlas™ Stent System.

1. Select an appropriate stent diameter based on reference vessel diameter, and select a stent length that is at least 8mm longer than the width of the aneurysm neck (in order to maintain a minimum of 4mm of stent length along the parent vessel on either side of the aneurysm neck). Refer to **Section 8, Device Description**, for additional stent sizing recommendations.
2. Follow the procedure outlined in the DFU regarding preparation, positioning and deployment of the Neuroform Atlas™ Stent System. In summary, these steps are as follows:
  - The sheath and delivery wire are used to transfer the Neuroform Atlas™ stent into a 0.0165" - 0.0170" ID microcatheter
  - After transfer, the sheath is removed from the proximal end of the delivery wire
  - The delivery wire is then used to advance the stent to the distal end of the microcatheter
  - The microcatheter, stent, and delivery wire are repositioned as a unit in order to ensure that the stent is located across the aneurysm
  - The stent is deployed across the neck of the aneurysm by stabilizing the delivery wire and withdrawing the catheter
3. The beginning of the procedure will be defined as the point in time when the first puncture or incision is made. The end of the procedure will be defined as the point in time when wound closure is complete. If these start and stop times are not documented in the nursing or anesthesia records, the time stamp of the initial procedural angiogram and final procedural angiogram will be used.

The following types of information will be collected regarding the implant procedure:

- Date of admission
- Procedure date, time, clinical site, investigator performing procedure
- Duration of procedure
- Device information
  - Neuroform Atlas™ Stent
  - Coil type used – brand/model
  - Adjunctive device use (e.g., balloon)
- Technical success of stent assisted coiling procedure
- Intra-operative AEs

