##### **Microcatheter**

## **SAfety and Effectiveness of the Treatment of Wide Neck, Saccular Intracranial Aneurysms with the Neuroform Atlas™ Stent System**

### **Short Study Name: ATLAS**

**Please note:** Similar to the 0.027" ID microcatheter that is used in conjunction with the Neuroform EZ Stent System, the 0.0165" - 0.0170" ID microcatheters used in conjunction with the Neuroform Atlas™ Stent System are sold separately and will not be part of the Neuroform Atlas™ Stent System.

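### Access-phase strokes and perforations enter no specified safety analysis if the procedure stops before a stent-system component enters, because ITT begins later than the procedure

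*Combined protocol and SAP*

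**What the plan says.** Section 3.8.2 fixes the start of the procedure: "The beginning of the procedure will be defined as the point in time when the first puncture or incision is made". Section 4.4 places a subject in ITT once implantation has been attempted, which it explains as "i.e., a component of the stent system was introduced into the body". Section 8.1, under Microcatheter, states that the microcatheters used with this stent "are sold separately and will not be part of the Neuroform Atlas™ Stent System".

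Section 4.4 also names a set called Enrolled Not Treated, for those who consented "but in whom no component of the Neuroform Atlas™ Stent System has ever been introduced into the body as part of an implantation procedure". It assigns that set no analysis. On the primary test it says: "The primary safety and effectiveness analyses will be performed on the mITT population". mITT requires a successful implant. Beyond the primary test, "safety data will include any adverse events reported to occur among ITT subjects in whom a Neuroform Atlas™ Stent implantation procedure was attempted" without success.

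Section 2.6 adds three rules:
- A consented subject who withdraws or is "found to be ineligible prior to initiation of the procedure will be considered a screening failure".
- "In all cases where subjects are consented but not treated using a Neuroform Atlas™ Stent, replacement subjects will be enrolled". Sections 2.6.3 and 3.3 repeat the replacement rule.
- A subject whose procedure is attempted but whose stent is not delivered is followed to the two-month visit as a treatment failure, with no 12-month primary endpoint evaluation.

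Section 6.1 requires every adverse event after consent to be recorded. Sections 4.7 and 4.8 require all subjects, and all reasons for exclusion from analysis, to be accounted for.

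**The concern.** The plan has two starting points, and a subject can be harmed between them. Vascular access and microcatheter placement belong to the procedure as Section 3.8.2 defines it, and Section 7.1 lists catheterization among the study risks. If the case is abandoned in that interval, the subject is too late to be a screening failure and too early to be ITT. An ITT safety analysis would not recover the event, because the subject is outside ITT. This is a separate matter from failed stent deliveries, which are inside ITT.

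The effect on reporting runs one way: procedural safety looks better than it was. Whether an event is counted also depends on how far the operator had got before stopping, which can differ between sites.

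The benchmark may count more broadly. In one of the balloon-assisted series used for the safety goals, Table 4 shows 66 of 75 aneurysms coiled, yet Table 6 reports complications over all 72 patients. The documents do not say at what stage the uncoiled cases stopped, so this is only suggestive.

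**Working it through.** **1. Where each subject lands under the text as written**

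| Procedure stops | Screening failure (2.6) | Set (4.4) | In primary safety rate | In added safety data | Replaced |
|---|---|---|---|---|---|
| Before first puncture | Yes, if withdrawn or ineligible | Enrolled Not Treated | No | No | Yes |
| After puncture, before any component enters | No | Enrolled Not Treated | No | No | Yes |
| After a component enters, stent not implanted | No | ITT | No | Yes | Yes |
| Stent implanted | No | ITT and mITT | Yes | Not needed | No |

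The second row is the gap. It exists because the stent travels through the microcatheter (Sections 3.8.2 and 8.1), so access and catheter placement come before the first component enters. An access-phase event in a subject who goes on to receive the stent is counted, in the last row.

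**2. Follow-up of the second row**

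Section 2.6 follows attempted procedures to two months. With the start point of Section 3.8.2, a punctured subject with no stent delivered fits that sentence. With the definition of attempted in Section 4.4, the subject does not. The text does not settle which applies.

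**3. The plan's own safety figures**

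- Enrollment per cohort: 153 / (1 − 0.15) = 180, as stated.
- The exact upper limit for x events in n is the 0.975 quantile of Beta(x + 1, n − x).
- Anterior, goal 20%: 20/153 gives 19.46% and passes; 21/153 gives 20.21% and fails. Power at 8% is P(X ≤ 20) = 98.9%.
- Posterior, goal 25%: 27/153 gives 24.63% and passes; 28/153 gives 25.35% and fails. Power at 12% is P(X ≤ 27) = 98.5%.

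Both agree with the stated value of approximately 99%.

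**4. Sensitivity of the primary result if such events were counted**

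The documents give no frequency, so k, the number of access-phase endpoint events, is an assumed range. Planning counts are 0.08 × 153 ≈ 12 and 0.12 × 153 ≈ 18. Each event adds one to numerator and denominator.

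| k | Anterior | Upper limit (goal <20%) | Posterior | Upper limit (goal <25%) |
|---|---|---|---|---|
| 0 | 12/153 | 13.3% | 18/153 | 18.0% |
| 1 | 13/154 | 14.0% | 19/154 | 18.6% |
| 3 | 15/156 | 15.4% | 21/156 | 19.8% |
| 5 | 17/158 | 16.7% | 23/158 | 21.0% |
| 10 | 22/163 | 19.7% | 28/163 | 23.9% |

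All pass. Only a result already at the limit is reversed by one event: 20/153 (19.46%) becomes 21/154 (20.09%), and 27/153 (24.63%) becomes 28/154 (25.19%).

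**5. Technical success**

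Sections 2.3.2 and 2.4.2.1 define it as a proportion of subjects without naming the set; Section 4.6.2 and Appendix B do not name one either. As an invented illustration, take 175 implants in 178 ITT subjects: 175/178 = 98.3%. Suppose 1% to 4% of 180 procedures, about 2 to 7, stop between puncture and component entry. The rate counted from puncture is then 175/180 = 97.2% down to 175/185 = 94.6%.

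**The case against.** The strongest reply is that these events are not hidden. The subjects belong to a set named in Section 4.4, their adverse events are recorded from enrollment (Section 6.1), and exclusions must be documented (Section 4.8). The CEC/DSMB reviews aggregate safety data with no stated restriction to ITT (Section 10.2). All of that stands, but none of it puts the event into a specified rate or summary.

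Second, the start point in Section 3.8.2 may be only a timing rule, since procedure duration is among the items then collected, and entering ITT at device entry is a deliberate choice in a single-arm device study. This also has force, and it is why the fix adds a set and leaves the ITT definition alone.

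Three stronger readings are tempting, and the documents do not support them:
- A reader might infer that these subjects are in no analysis set. They are in Enrolled Not Treated; what is missing is an analysis of it.
- A reader might infer that they have no follow-up. Section 2.6 can be read as giving them two months.
- A reader might infer that the primary safety test is compromised. Suppose the true rate from puncture equals the goal t and a fraction f of subjects has an excluded endpoint event. The rate among the rest is then (t − f)/(1 − f). For f of 1% to 3%, the chance of passing rises from 1.7% to 3.0–8.6% (anterior) and from 2.0% to 3.2–7.9% (posterior). But f is assumed throughout, the primary test is defined on implanted subjects, and the fix leaves that test unchanged.

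**Conclusion.** The gap is real and follows from the plan's own definitions. A consented subject who has a stroke or perforation after puncture, and whose procedure stops before any stent-system component enters, is replaced and contributes to no specified safety analysis. The bias is in the favourable direction. It affects supportive procedural safety reporting and, if ITT is used as the denominator, technical success.

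Its size cannot be derived from the documents. At the planning rates the primary conclusion withstands even ten such events per cohort; it would turn on one event only at the decision limit. This is a correctable reporting gap and an inconsistency over when a procedure counts as attempted. It does not show that the primary result would change.

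**What to change.** Keep the primary analysis on mITT. In Section 4.4, add a supportive safety set of all consented subjects from first puncture or incision with intent to implant. Report adverse events, major ipsilateral stroke and neurological death in that set beside the mITT result. In Sections 2.4.2.1 and 4.6.2, name it as the technical-success denominator, or report technical success on both it and ITT. Reconcile Sections 2.6, 3.8.2 and 4.4 on when a procedure counts as attempted, so that it is clear whether the two-month follow-up covers these subjects.

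The cost is amendment wording and, on the assumed range above, a few extra subjects in a table. Supportive safety and technical-success figures may become slightly less favourable. The synopsis records anterior approval in May 2019, so for that already analysed cohort the summary would be retrospective and should be labelled so.
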